7.3. Assessment of Adverse Events

All AEs will be assessed by the Investigator and recorded in the CRF, including the dates of onset and resolution, severity, relationship to study medication, outcome, and action taken with study medication.

7.3.1. Severity

The term “severe” is often used to describe the intensity (severity) of a specific event (as in mild, moderate, or severe myocardial infarction); the event itself, however, may be of relatively minor medical significance (such as severe nausea). This is not the same as “serious,” which is based on subject/event outcome or action criteria usually associated with events that pose a threat to a subject’s life or functioning. The severity of AEs will be assessed according to the following definitions:

- **Mild:** The AE is noticeable to the subject and/or the Investigator but does not interfere with routine activity.
- **Moderate:** The AE interferes with routine activity but responds to symptomatic therapy or rest.
- **Severe:** The AE significantly limits the subject’s ability to perform routine activities despite symptomatic therapy.

7.3.2. Causal Relationship to Study Medication

The Investigator’s assessment of causality is based on clinical judgment regarding the reasonable possibility that the study medication caused the event and may include consideration of some or all of the following factors:

- Possible alternative causes of the AE, including the disease under treatment, comorbid conditions, other medications, and environmental factors.
- The temporal association between drug exposure and onset of the AE.
- Whether the clinical or laboratory manifestations of the AE are consistent with known actions or toxicity of the study medication.
- Whether the AE resolved or improved with decreasing the dose or stopping the study medication (“de-challenge”) or recurred or worsened upon re-exposure to the study medication (“re-challenge”).

The causal relationship between the study medication and the AE will be described using one of the following categories:

- **Not Related:** Evidence exists that the AE has an etiology other than the study medication (such as a preexisting condition, underlying disease, intercurrent illness, or concomitant medication).
- **Related:** A temporal relationship exists between the event onset and administration of the study medication. It cannot be readily explained by the subject's clinical state or concomitant therapies and appears with some degree of certainty to be related based on the known therapeutic and pharmacologic actions of the drug. In case of cessation or reduction of the dose, the event abates or resolves and reappears upon re-challenge. It should be emphasized that ineffective treatment should not be considered as causally related in the context of AE reporting.

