7.4.3. Serious Adverse Event and Adverse Event of Special Interest Reporting Timeline

All SAEs and AESIs must be reported to Clinical Safety and Pharmacovigilance within 24-hours of the time the Investigator or his/her designee becomes aware that an SAE or AESI has occurred, whether or not the event is considered to be related to study medication. If the initial SAE or AESI is reported by telephone, a written report signed by the Investigator must be submitted within 24-hours.

The SAE/AESI Report Form must be completed in accordance with the SAE/AESI Report Form Completion Guidelines. If all information on the SAE/AESI Report Form is not available at the time of the initial report, follow-up SAE or AESI reports will be completed and submitted.

To report an SAE or AESI, complete and send the SAE/AESI Report Form to the following:

Theravance Biopharma Clinical Safety
[contact]
Email: [contact]

For medical questions regarding an SAE or AESI, contact the medical monitor by telephone as follows:

Medical Monitor Contact Information:

[contact] (US) /
[name] (Ireland)

Email: [contact]

For sites located in Mexico, Peru, Chile or Argentina:

Email: [contact]

For fatal or life-threatening events, also fax copies of hospital case reports, autopsy reports, and other documents when requested. Additional information may be requested from the Investigator to ensure the timely completion of accurate safety reports.

An SAE may qualify for reporting to regulatory authorities if the SAE is possibly attributable to the study medication and is unexpected/unlisted based on the current TD-9855 IB. In this case, all Investigators will receive notification of the event. The Investigator is responsible for notifying the Institutional Review Board or Ethics Committee and documenting the notification, as required by local regulatory authorities and in accordance with the local institutional policy.

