9.1. Adverse Events

Adverse events are collected from signing of the informed consent form through the end of follow-up. Adverse events will be coded to the preferred terms of the Medical Dictionary for Regulatory Activities (MedDRA®, version 24.1).

A treatment-emergent adverse event (TEAE) will be defined as any AE that begins on or after the date of first dose of study drug up through 14 days after the date of last dose of study drug. AEs that begin more than 14 days after the date of last dose of study drug and AEs that begin during the period from obtaining informed consent to the start of administration of study drug will not be considered treatment-emergent and will be listed only.

The following AE summaries will be provided for each treatment period:

- TEAE overall summary
- TEAEs by preferred term
- TEAEs by system organ class and preferred term
- Moderate or severe TEAEs by system organ class and preferred term
- TEAEs by preferred term with frequency > 3% of safety analysis set subjects
- TEAEs by system organ class, preferred term, and severity
- Drug-related TEAEs by system organ class and preferred term
- Drug-related TEAEs by system organ class, preferred term, and severity
- Drug-related moderate or severe TEAEs by system organ class and preferred term
- Serious TEAEs by system organ class and preferred term
- Drug-related serious TEAEs by system organ class and preferred term
- TEAEs resulting in on-study deaths
- TEAEs leading to premature study drug discontinuation
- TEAEs leading to temporary interruption of study drug
- TEAEs of special interest by system organ class and preferred term (Section 9.1.1)

If no adverse events meeting a specific table definition were reported, the body of the table will contain only a statement that no events met the table definition.

The following AE listings will be provided:

- TEAEs
- AEs leading to premature study drug discontinuation
- AEs resulting in temporary interruption of study drug
- Serious adverse events
- Deaths
- Non-treatment-emergent adverse events
- Adverse events of special interest (Section 9.1.1)
- Adverse events for excluded site 27045 (Section 6.2.1)

9.1.1. [REDACTED]

[REDACTED]

- [REDACTED]
- [REDACTED]
- [REDACTED]
- [REDACTED]
- [REDACTED]
- [REDACTED]

[REDACTED]

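### The two causality categories in Protocol 7.3.2 leave a gap and depart from the section's own reasonable-possibility standard, so drug-related AE tables may under-count

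*Protocol*

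**What the plan says.** Protocol Section 7.3.2 first sets a broad standard. The investigator's causality assessment "is based on clinical judgment regarding the reasonable possibility that the study medication caused the event". The choice of what to weigh is left open: the assessment "may include consideration of some or all of the following factors". The list that follows names alternative causes, timing, consistency with the known actions or toxicity of the drug, and de-challenge or re-challenge.

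The section then states that the relationship "will be described using one of the following categories", and gives two:

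- **Not Related:** "Evidence exists that the AE has an etiology other than the study medication".
- **Related:** there is a temporal relationship, and the event cannot readily be explained by the subject's clinical state or other therapies and "appears with some degree of certainty to be related based on the known therapeutic and pharmacologic actions of the drug". A further sentence reads "In case of cessation or reduction of the dose, the event abates or resolves and reappears upon re-challenge".

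Protocol Section 7.4.2 makes Section 7.3.2 the guideline for the recorded causality. The field feeds the study-medication-related tables in Protocol Section 8.6.2 and four summaries in SAP Section 9.1: drug-related TEAEs, the same by severity, those that are moderate or severe, and "Drug-related serious TEAEs by system organ class and preferred term". Section 7.4.2 also lets investigators report SAEs they consider related for 30 days after the last study visit.

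**The concern.** The category definitions do not apply the standard that introduces them. Consistency with known pharmacology is one optional factor in the list but becomes a condition of Related. De-challenge and re-challenge are also optional in the list, yet they reappear in the definition for any event after which dosing stopped or was reduced. Not Related is not the complement of Related, because it calls for positive evidence of another cause.

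An investigator facing an event between the two definitions must still pick one, and the protocol gives no rule for doing so. Two sites could code the same event differently. Safety and tolerability is one of the primary objectives (Protocol Section 2.1), and the drug-related tables are a routine summary of it. The late-SAE window raises a separate issue: there the category decides whether the report falls within the provision at all, so a gap event judged Not Related could be missing from the database and not merely placed in a different table.

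**Working it through.** No figure is stated and no arithmetic applies. The check sets the two definitions against types of event, and then traces where the category is used.

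**Fit of the definitions**

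1. *Evidence of another cause.* Not Related applies.
2. *Plausible timing, no alternative explanation, consistent with known drug actions, dosing continued.* Related applies. The re-challenge sentence is not engaged, because it begins with the case of cessation or dose reduction.
3. *Plausible timing, no alternative explanation, no known mechanism.* Related fails on the pharmacology condition. Not Related fails because there is no evidence of another cause. The event fits neither, although the opening standard could support Related.
4. *As in 2, but dosing was stopped permanently and the event resolved.* The literal re-challenge sentence cannot be met. Not Related still lacks evidence. The event fits neither.
5. *Implausible timing, no cause identified.* Related fails on timing and Not Related fails for want of evidence. The event fits neither.

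Types 3 to 5 show that the categories are not exhaustive. Types 3 and 4 also show that they conflict with the section's opening standard.

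**How often re-challenge could occur**

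Protocol Section 3.1 bars dose reduction. Under Section 6.8.1, a subject who meets a stopping rule stops dosing and leaves the study. Re-exposure is therefore possible mainly after a temporary interruption, which Protocol Section 8.6.2 and SAP Section 9.1 do foresee. Type 4 is thus the usual situation for an event that ends treatment.

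**Direction**

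A type 3 or 4 event judged reasonably possible is counted correctly if coded Related and lost from the drug-related tables if coded Not Related. A type 5 event could be added wrongly if coded Related. The text sets no default for any of them. Under-counting is therefore possible, but neither its direction overall nor its size follows from the documents.

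**Where the category is used**

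- *Dependent on it:* the related-event tables in Protocol 8.6.2, the four drug-related summaries in SAP 9.1, and the 30-day window in Protocol 7.4.2.
- *Not dependent on it:* SAP 9.1 tables of all TEAEs, serious TEAEs, discontinuations, deaths and AESIs; and SAE/AESI reports to the sponsor, due within 24 hours whatever the causality (Protocol 7.4.3).

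**The case against.** The best defence is that the opening sentence governs. Causality is clinical judgment of what is reasonably possible, Section 7.4.2 calls Section 7.3.2 guidelines, and nothing says the category text overrides the opening. On that view a sensible investigator codes a gap event as Related and the definitions are only descriptive. The re-challenge sentence is also conditional, so it is not a universal requirement. Impact is limited: no hypothesis test or endpoint uses the field, and the randomized period has a placebo column (SAP Section 6.1) for comparing all TEAEs without attribution.

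Much of this stands. It limits the consequence but does not remove the conflict. The definitions still contradict the opening, and the protocol does not say which prevails.

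A reader might go further and infer that an unexpected reaction can never be classed as related and that expedited reports will be too few. The documents do not support that:

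- Unexpected in Section 7.4.3 means not listed in the Investigator's Brochure, which is not the same as lacking a known mechanism.
- The regulatory trigger is broader than the Related definition: "An SAE may qualify for reporting to regulatory authorities if the SAE is possibly attributable to the study medication and is unexpected/unlisted". Section 7.4.3 does not tie it to the recorded category.
- Sponsor Drug Safety may independently unblind cases for SUSAR reporting (Protocol Section 3.5.1).

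**Conclusion.** The concern holds in a limited form. The two categories are not exhaustive and are inconsistent with the reasonable-possibility standard of the same section. Events with plausible timing, no alternative cause and no known mechanism, and events that resolved after permanent discontinuation, fit neither definition as written. The result may be inconsistent classification, and possible under-counting in the drug-related tables and among late related SAEs.

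No number can be put on this. The documents do not say how many events would fall in the gap or how sites would resolve them, and any percentage would be invented. The conclusion assumes that at least some investigators apply the category text literally; if all of them follow the opening sentence, the effect is nil.

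**What to change.** Base both definitions in Protocol Section 7.3.2 on the opening standard. An event is Related when causation by study medication is a reasonable possibility, and Not Related when it is not. Remove the pharmacology and re-challenge wording from the Related definition. Known pharmacology, de-challenge and re-challenge are already in the bulleted list and should stay there as supporting factors only.

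Leave the regulatory trigger in Section 7.4.3 unchanged. Replacing it with the recorded category would look tidier, but it would tie regulatory reporting to a two-way entry and narrow a safeguard.

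The cost is a wording change and a memo to sites, with no new data collection. Drug-related counts may rise somewhat. If the change is made while the trial is running, two standards would be mixed in one table. Events already recorded would then need reassessment, or the drug-related tables must carry a footnote giving the date of the change.

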7.4. Adverse Event Reporting and Recording

7.4.1. Adverse Event Reporting

Timely, accurate, and complete reporting and analysis of safety information from clinical trials is crucial for the protection of subjects and is mandated by regulatory agencies. The sponsor has established standard operating procedures (SOPs) in compliance with regulatory requirements worldwide to ensure appropriate reporting of safety information. All clinical trials sponsored by Theravance Biopharma will be conducted in accordance with these procedures.

7.4.2. Adverse Event and Serious Adverse Event Recording

All AEs, regardless of seriousness, severity, or causal relationship to study medication, will be recorded from signing informed consent through the last study visit (or last subject contact in the case of a follow-up telephone call). The AEs will be recorded on the AE page of the CRF. The SAEs, regardless of relationship to study medication will be recorded from signing informed consent through the last study visit (or last subject contact in the case of a follow-up telephone call). ****Exception for Subjects entering from Study 0169 (0169 Completers Group):*** Adverse Events, including Serious Adverse Events, that start after the Study 0170 ICF is signed, but before the first dose on Study 0170 is taken, are considered events originating in Study 0169. Additionally, Investigators may report SAEs assessed as related to study medication through 30 days following the last study visit (or last subject contact in the case of a follow-up telephone call). All SAEs will be recorded on both the SAE/AESI Report Form and the AE page of the CRF and should include the following:

Description of event:

- Signs and symptoms due to a common etiology should be reported as a single diagnosis; for example, cough, runny nose, sneezing, sore throat, and head congestion would be reported as “upper respiratory infection.”
- A diagnosis or description must be as specific and as complete as possible (e.g., “lower extremity edema” instead of “edema”).
- Hospitalization or surgical procedures should not be used as AE terms (e.g., if a subject was hospitalized for cholecystectomy due to cholecystitis, the AE term should be recorded as cholecystitis, and not as the procedure, cholecystectomy).
- “Death” should not be used as an AE term unless the cause of death is unknown. For events with a fatal outcome, the cause of death should be the AE term (e.g., if a subject died of an acute myocardial infarction, the AE term should be recorded as “Myocardial Infarction” and the event outcome as fatal).

Relationship to study medication: The Investigator will make an assessment of the causal relationship of the study medication to the AE using the guidelines in Section 7.3.2.

Severity: The severity of the AE will be assessed using the guidelines in Section 7.3.1.

Outcome: The outcome of AEs will be recorded.

Therapeutic measures: Measures taken for the treatment or management of the AEs will be recorded.

7.4.3. Serious Adverse Event and Adverse Event of Special Interest Reporting Timeline

All SAEs and AESIs must be reported to Clinical Safety and Pharmacovigilance within 24-hours of the time the Investigator or his/her designee becomes aware that an SAE or AESI has occurred, whether or not the event is considered to be related to study medication. If the initial SAE or AESI is reported by telephone, a written report signed by the Investigator must be submitted within 24-hours.

The SAE/AESI Report Form must be completed in accordance with the SAE/AESI Report Form Completion Guidelines. If all information on the SAE/AESI Report Form is not available at the time of the initial report, follow-up SAE or AESI reports will be completed and submitted.

To report an SAE or AESI, complete and send the SAE/AESI Report Form to the following:

Theravance Biopharma Clinical Safety
[contact]
Email: [contact]

For medical questions regarding an SAE or AESI, contact the medical monitor by telephone as follows:

Medical Monitor Contact Information:

[contact] (US) /
[name] (Ireland)

Email: [contact]

For sites located in Mexico, Peru, Chile or Argentina:

Email: [contact]

For fatal or life-threatening events, also fax copies of hospital case reports, autopsy reports, and other documents when requested. Additional information may be requested from the Investigator to ensure the timely completion of accurate safety reports.

An SAE may qualify for reporting to regulatory authorities if the SAE is possibly attributable to the study medication and is unexpected/unlisted based on the current TD-9855 IB. In this case, all Investigators will receive notification of the event. The Investigator is responsible for notifying the Institutional Review Board or Ethics Committee and documenting the notification, as required by local regulatory authorities and in accordance with the local institutional policy.

7.5. Adverse Event Follow-up

A subject experiencing an AE, AESI, or SAE will be followed by the Investigator or his/her trained delegate(s) through the follow-up visit or until the Investigator and/or the sponsor has determined that the AE, AESI, or SAE has resolved or a stable clinical endpoint is reached, whichever is longer. The sponsor may request follow-up of certain AEs until resolution and documentation of assessments made during this period.

The Investigator must take all therapeutic measures necessary for resolution of an AE. Any medications necessary for treatment of the AE must be recorded in the concomitant medication section of the CRF.

8. STATISTICAL CONSIDERATIONS

8.1. General Considerations

All data for each subject will be listed as collected. All statistical summaries and analyses will be performed using SAS software (SAS Institute, Cary, North Carolina, US).

Continuous data will be summarized using an 8-point descriptive summary (n, mean, standard deviation, median, interquartile range [25% quartile, 75% quartile], minimum, and maximum) unless otherwise specified in the statistical analysis plan (SAP) or table shell. Categorical data will be summarized using counts and percentages.

For analysis, Day 1 is defined as the day of the first study medication dose. The preceding day is Day -1.

Baseline is the last assessment (scheduled or unscheduled) obtained before start of study medication dosing for each phase of the study (OL or double-blind randomized withdrawal phase), unless otherwise specified in the SAP. Baseline for endpoints that have more than one component is calculated from the individual component baselines, whether or not they were assessed during the same visit.

Any changes to the data summaries and analyses outlined in this section will be described in the applicable SAP. Any changes to the definition of the endpoints will also be included in a protocol amendment.

8.2. Sample Size and Power

Assuming that 60% are eligible for randomization at the end of the 16-week OL period, approximately 258 subjects will be enrolled such that 154 subjects are expected to continue into the randomized treatment period. For the De Novo Group, the goal is to enroll at least 40% of MSA subjects.

The primary analysis will occur when all subjects in the Full analysis set (FAS) (Section 8.3.2) of double-blinded randomized withdrawal phase of the study have either completed the primary endpoint assessment (OHSA#1 and PGI-S at Week 6 post randomization) (V9, D155) or discontinued earlier and the database has been cleaned and locked. A sample size of 154 at randomization will provide an overall power of 90% to detect a difference of 25% (25% TD-9855 vs. 50% PBO) in the primary endpoint of proportion of subjects that meet the criteria of treatment failure at Week 6 (V9, D155) during the double-blind randomized withdrawal phase at two-sided alpha level of 0.05.

8.3. Analysis Sets

All efficacy analyses in the double-blind randomized withdrawal phase will be performed based on the FAS using the assigned randomized treatments. The FAS of the double-blind randomized withdrawal phase is defined as all randomized subjects who have received at least 1 dose of study medication post randomization.

The per-protocol (PP) analysis set of the double-blind randomized withdrawal phase comprises all subjects in the FAS with no major analysis protocol deviations (Section 8.3.2). If the number of FAS subjects excluded from the PP analysis set is <5% per treatment group, PP analyses will not be performed. Otherwise, both the FAS and the PP analysis set will be used for selected efficacy summaries and analyses.

The safety analysis set (Safety set) of the double-blind randomized withdrawal phase is comprised of all randomized subjects who receive at least 1 dose of study medication. The safety analysis set will be the analysis set for both general (baseline, exposure, and compliance) and safety analyses in the double-blind randomized withdrawal phase. Subjects in the safety analysis set will be grouped according to the actual study treatments they receive.

The FAS and Safety set for OL phase will be identical and is defined as all enrolled subjects who have received at least one dose of TD-9855.

